## **FULL PROTOCOL TITLE:** Toric Contact Lens Performance Study

### **1.0 Objectives**

This study seeks to quantify the near visual performance and subjective visual acceptance of toric contact lenses as compared to spherical lenses in an astigmatic cohort of patients.

**Study Hypotheses:** Subjects will have better near visual acuity and near visual performance with toric, as opposed to spherical, contact lens correction. As such, the following hypotheses will be tested:

- $H_{01}$ : There is no statistically significant difference in near visual acuity or near vision performance between contact lenses corrections
- $H_{a1}$ : There is a statistically significant difference in visual acuity or vision performance between contact lenses corrections

### **2.0 Background**

Americans spend over 10 hours a day consuming media on smartphones, digital tablets and home computers. The visual demands of this type of work require the use of sustained clear near and intermediate vision. Previous work in our labs has shown small but measureable improvements in visual acuity for multifocal contact lenses as compared to monovision and toric lenses as compared to spherical correction; especially in low lighting or low contrast conditions. Unfortunately standard in office high contrast, high luminance testing is often not helpful in demonstrating potential improvement in real-world tasks afforded by toric lenses.

Woods et al began exploring patients' preferences conducting real-world tasks such as the ability to locate a web page, read a newspaper or use a computer. They showed that while the difference in standard acuity testing were small, patients reported significant subjective improvements in driving, watching a television, and using a desktop computer, among others.

Wolffsohn and colleagues recently developed iPad based applications that can quantify reading performance on digital devices while the user performs reading tasks (see also Appendix). The user's face is analyzed in real-time by the front facing camera to allow working distance and blinks to be tracked. Swipes, changes in magnification and the time to complete the task are also assessed. This group also developed a Near Activity Visual Questionnaire (NAVQ) to quantify subjective near visual function.

The purpose of the proposed study is to quantify subjective and objective benefits of toric corrections in astigmatic patients, , using the latest digital and patient reported outcomes tools.

### **3.0 Inclusion and Exclusion Criteria**

#### **ALL SUBJECTS**

- Able to read and understand the study informed consent

## **FULL PROTOCOL TITLE:** Toric Contact Lens Performance Study

- +0.50 to +4.00 or -0.50 to -6.00 D vertex corrected sphere power
- Best corrected acuity of 20/25 or better in each eye
- Self report of at least 5 hrs/day using digital devices
- No history of ocular pathology or surgery
- No active ocular infection or clinically significant ocular inflammation
- No significant binocular vision abnormality
- No gas permeable lens wear for at least 3 months
- Not an optometrist or optometry student
- Not pregnant/lactating (by self-report)
- 18 to 39 years of age (inclusive)
- 0.75 to 1.50 D vertexed refractive cylinder OD and OS

Potential subjects will be initially screened for study eligibility by phone/in person discussion and through collection of baseline data at visit 1.

### *Vulnerable Populations*

The following vulnerable populations will be excluded from the study:

1. Adults unable to consent
2. Individuals who are not yet adults (infants, children, teenagers under age 18)
3. Prisoners
4. Students for whom the principal investigators have direct access to/influence on grades.
5. Pregnant/lactating women (by self-report)

## **4.0 Number of Subjects**

The proposed single-site study will be conducted at The Ocular Surface Institute at the University of Houston College of Optometry. Up to 76 subjects will be screened for study inclusion, with the goal of completing 34 subjects.

Source data will be collected on paper case report forms and then doubly entered electronically into a database by trained personnel. Source data will be quality assured at the levels of coding, scoring, and entry prior to locking the dataset for analysis.

In this within-subject crossover design, a paired t-test will be used to compare primary outcome visual acuity performance of study treatment lens wear to standard spherical contact lens wear among astigmats. We will use a two-sided independent t-test to ensure there are no carry over or period effects in our cross-over design, although it is not anticipated. As a secondary outcome, subjects will be asked their preference of contact lenses in a two-alternative forced choice format. A one-sample binomial test will be used to test the hypothesis that the probability of preference to treatment lens and standard lenses are equally likely ( $H_0: p=.5$  v.  $H_1: p\neq.5$ ).

## FULL PROTOCOL TITLE: Toric Contact Lens Performance Study

We aim to test the hypothesis that  $H_0: \Delta=0$  v.  $H_1: \Delta\neq0$  using a two-sided test with significance level  $\alpha=0.05$ , where  $\Delta$  is the underlying benefit for treatment contact lenses versus spherical contact lenses in this cross-over design. Based on previous studies reported average photopic low contrast visual acuity ranged from 0.3 to 0.4 logMAR with various brands of toric contact lenses and under the same conditions from 0.51 to 0.56 with spherical contact lenses among low-to-moderate astigmatic eyes. An estimated improvement with toric lenses has been reported as  $0.07\pm0.14$  among those with low astigmatism with the magnitude of improvement increasing among those with high levels of astigmatism. It is reasonable to expect a detectable range of 2 letters to half-line of improvement with the treatment contact lenses versus the standard sphere lenses. If we expect a half-line treatment benefit and the within-subject variance of the difference in mean visual acuity between the two periods to be a line (0.1 logMar), then based on pilot-study results, and a required 80% power we need 34 participants overall for each study population (68 total). We will randomize an equal number of subjects to each group (i.e., group A receives treatment 1 in period 1 and treatment 2 in period 2; group B receives treatment 2 in period 1 and treatment 1 in period 2). Depending on the variability, a sample size of 34 in each sampled population allows us to detect a smaller effect size (e.g., high contrast tests) as low as 2.5 letters with a within-subject variability of 0.06 logMar. The visual function testing is novel and has not been used on a population of astigmatic contact lens wearers. So sample size planning cannot be done for these tests. We plan to screen up to 38 participants from the study population to allow for attrition.

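### Section 4.0 gives conflicting sample sizes (34 and 68) and screening caps (76 and 38) for a trial with one population and one comparison

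*Protocol*

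**What the plan says.** All the figures are in protocol section 4.0 (Number of Subjects).

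- Opening paragraph: "Up to 76 subjects will be screened for study inclusion, with the goal of completing 34 subjects".
- Power paragraph, requirement: "we need 34 participants overall for each study population (68 total". The per-population wording returns a few lines later: "a sample size of 34 in each sampled population allows us to detect".
- Power paragraph, last sentence: "We plan to screen up to 38 participants from the study population to allow for attrition". Here the population is singular.
- Variability behind the 34: "the within-subject variance of the difference in mean visual acuity between the two periods to be a line (0.1 logMar".

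The rest of the protocol describes one population and one comparison. Section 1.0 names a single astigmatic cohort. Section 3.0 has one eligibility list for all subjects, which requires 0.75 to 1.50 D of cylinder in both eyes. Section 4.0 sets the study lens against "standard spherical contact lens wear among astigmats". Section 6.0 compares toric with spherical lenses only, and the lens table in section 9.0 has one arm label covering a toric and a sphere lens. The groups A and B of section 4.0 are the two crossover sequences, not populations. The SAP gives no sample size.

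**The concern.** The same verb, screen, carries two caps, one exactly twice the other. The stated goal of 34 completers is half the stated overall need of 68. A trial that finishes 34 subjects has met its target by the opening paragraph and reached half of it by the power paragraph. A reader also cannot tell when screening should stop, or compare actual subject flow with a plan. Separately, a variance given in logMAR cannot be used as printed: variances are in squared units, and the literal value does not lead to 34.

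**Working it through.** **Inputs, all from section 4.0:** paired t-test, two-sided alpha 0.05, power 80%, half-line benefit = 0.05 logMAR (the text equates one line with 0.1 logMAR), variability 0.1 logMAR.

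**Step 1. Reproduce the 34.** Take 0.1 logMAR as the SD of the within-subject difference, so the standardized difference is 0.05/0.10 = 0.5.

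- Normal approximation: n = (1.960 + 0.842)² × (0.10/0.05)² = 31.4, so 32.
- Exact noncentral t, with noncentrality 0.5 × √n on n − 1 df: at n = 34 the noncentrality is 2.915 and power is 80.8%; at n = 33 power is 79.5%. The smallest n for 80% is 34.
- With n − 2 df for the crossover the answer is still 34 (80.7%).

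So 34 is the requirement for one population analysed by one paired comparison.

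**Step 2. Test whether 68 can be the requirement for that same population.**

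| Reading of 0.1 | SD of difference | n for 80% power |
|---|---|---|
| SD of the difference | 0.100 | 34 |
| SD within each period | 0.1 × √2 = 0.141 | 65 |
| Literal variance of the difference | √0.1 = 0.316 | 316 |

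No reading gives 68. The 65 is close, but the text refers 0.1 to the difference between periods and presents 68 as 34 for each population. Under the first reading, 68 completers give noncentrality 0.5 × √68 = 4.123 and power 98.2%, not 80%. Under the literal variance, 34 completers give 14.6%.

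**Step 3. Relate the four figures.** 2 × 34 = 68 and 2 × 38 = 76. With two populations, 68 needed and 76 screened agree with 34 and 38 for each, but the goal of 34 completers is then wrong and the second population is undefined. With one population, 34 and 38 agree, and 68 and 76 are unexplained.

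**Step 4. Room for losses under each pairing.**

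| Screening cap | Target | Allowance |
|---|---|---|
| 38 | 34 | 4 (4/38 = 10.5%) |
| 76 | 34 | 42 (42/76 = 55.3%) |
| 76 | 68 | 8 (8/76 = 10.5%) |

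**Step 5. Can this be turned into power?** Not from the documents, which state no screen-failure or dropout rate. Suppose 38 caps screening, and average the Step 1 power over a binomial number of completers. Assumed combined losses of 5% to 20% give 83.1% to 75.8%. Assumed screen failure of 40% to 50% followed by 10% dropout leaves 38 × 0.60 × 0.90 = 20.5 to 38 × 0.50 × 0.90 = 17.1 expected completers, and about 57% to 49% power. The answer is set by the assumption.

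**The case against.** The strongest reply is that the target is not really in doubt. The goal of 34 completers is explicit, 34 recurs in the power paragraph, it reproduces from the stated inputs, and the last sentence of that paragraph speaks of one population. That stands: 34 is the power-based total. It leaves the total of 68 and the per-population wording as errors, and it does not settle the screening cap.

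A second reply is that the figures describe a flow of 76 screened, 38 randomized and 34 completed, with "We will randomize an equal number of subjects to each group" giving 19 per sequence. A reader might infer this, but the text says that up to 38 will be screened, not randomized. Nothing shows that the verb is a slip. Section 3.0 says "Potential subjects will be initially screened for study eligibility by phone/in person discussion and through collection of baseline data at visit 1", and in section 7.0 the eligibility check follows consent and testing at visit 1, so attrition from 38 could include screen failures.

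A reader might infer the opposite: that 68 and 76 are both left over from a two-population design, a view helped by the mention of multifocal lenses in section 11.0. The exact doubling makes this plausible, and it would leave 38 as the cap, but no document says so.

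Finally, the SAP is in the past tense and section 5.0 expected analyses to finish in August 2018, so the correction may serve reporting only. That is fair. It limits the practical effect but does not remove the contradiction.

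**Conclusion.** The contradiction holds, and section 4.0 is wrong as written. For the design described, the requirement is 34 completers in total (80.8% power), provided that 0.1 logMAR is the SD of the within-subject difference. The unit, and the later use of 0.06 logMAR as a within-subject variability, support that reading. The total of 68 and the word variance do not fit the design.

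Which of 76 and 38 is the screening cap cannot be settled from the documents. The supported size of the problem is the spread in the loss allowance: 4, 8 or 42 subjects, depending on the pairing.

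Two stronger conclusions are tempting. One is that the trial is underpowered. The documents do not show this: the calculation is sound on the SD reading, and the 316 and 14.6% belong to a literal reading that the unit argues against. The other is that the effect on power is known to be modest, or known to be large. Neither is shown, because the result depends on loss rates that the documents do not give. This is a certain defect of clarity and reporting that should be corrected, and its effect on power cannot be quantified.

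**What to change.** In section 4.0:

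1. Delete the two phrases that make 34 a per-population figure, and the total of 68. If a second population is intended, define it and correct the goal of 34 completers in the opening paragraph instead.
2. Keep 34 completers as the single power-based total.
3. Describe 0.1 logMAR as the SD of the within-subject difference, not a variance.
4. Have the sponsor reconcile 76 and 38 by giving one number each for screened, randomized and completed, with the assumed screen-failure and dropout rates.

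Items 1 to 3 change wording only if there is one population, and leave the requirement at 34. Item 4 needs a decision by the sponsor. It may be more than wording, because treating 38 as a number randomized rather than screened could raise how many subjects are fitted with lenses. If recruitment has closed, make the same correction and report the actual screened, randomized and completed counts against the target of 34.

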## 5.0 Recruitment Methods

Potential subjects will be recruited from the patients and staff of the University Eye Institute/University of Houston College of Optometry, as well as the surrounding community via verbal communication, print media (e.g. study fliers, newspaper adverts), telephone and electronic media (e.g. email, The Ocular Surface Institute Website, social media). Additionally, potential subjects will be identified and recruited via The Ocular Surface Institute's research database.

The total duration of an individual subject's participation in the study will be less than 1 month. The study will consist of 5 visits. Visit 1 will be a baseline evaluation, pre-fitting assessment, randomization, and contact lens fitting. Visits 2 and 4 will be contact lens follow-ups. Visits 3 and 5 are outcome visits. Expected visit timing is summarized in the table below:

Anticipated Visit Timing and Duration		
Study Window	Study Visit	Duration
Day 1	Visit 1: Baseline, randomization, contact lens fitting	120 minutes
Day 4 ± 2	Visit 2: Contact lens follow-up	30-50 minutes
Day 10 ± 2	Visit 3: Outcome lens #1, re-fit to lens #2	75 minutes
Day 13 ± 2	Visit 4: Contact lens follow-up	30-50 minutes

## FULL PROTOCOL TITLE: Toric Contact Lens Performance Study

Day 20 ± 2	Visit 5: Outcome lens #2	55 minutes
------------	--------------------------	------------

The anticipated duration to enroll and complete all study subjects is approximately 6 months. The estimated date for the investigators to complete analyses for this study is August 2018.

## 6.0 Study Endpoints

The primary study endpoints will compare toric to spherical lenses for:

- Binocular near visual acuity

The secondary study endpoints will compare toric to spherical lenses for:

- Binocular near visual performance
  - Reading speed, errors, etc.
- Contrast
  - Binocular low contrast acuity, contrast sensitivity at near

## 7.0 Procedures Involved

The study is a clinical trial. Subjects will be randomized to start with either toric lenses or spherical correction. Patients will be seen for 5 visits over a period of approximately 1 month. Visit 1 will determine subject eligibility for the study. Visits 2 and 4 are contact lens follow-up visits. Visits 3 and 5 are study outcome visits. Tests of visual performance at a near reading distance will be evaluated with an iPad application (Optom Central) developed by [name]. This application can measure reading speed, near contract sensitivity and can provide information on how a subject interacts with the electronic device (e.g. blink rate, working distance from the device, scrolling and zooming on the page, etc.). This application is designed for research purposes only and is not commercially available in the Apple App Store.

Visit 1: Screening, Enrollment and Baseline		
Step	Item	Details
1.1.1	Informed Consent	Review and complete the informed consent form
1.1.2	Subject Demographics	Collect subject demographic data
1.1.3	Medical/Ocular History	Collect subject history including contact lens history
1.1.4	Concomitant Medications	Collect information on concomitant medications
1.1.5	Distance and Near Visual Acuity	Perform Distance and Near Snellen and LogMAR acuity OD/OS with the patient's habitual correction.
1.1.6	Questionnaires	Administer the NAVQ to the subject

**FULL PROTOCOL TITLE:** Toric Contact Lens Performance Study

1.1.7	Contrast Sensitivity	Perform the contrast sensitivity test on the iPad
1.1.8	Radner reading test	Perform the Radner reading speed test on the iPad
1.1.9	Functional Vision testing with iPad	Perform the functional vision test on the iPad
1.1.10	Auto-Refraction / Auto-keratometry	Perform autorefraction/keratometry with open field machine
1.1.11	Refraction	Perform Manifest Refraction using maximum plus to best visual acuity
1.1.12	Accommodation, binocular vision	Conduct negative relative accommodation and positive relative accommodation test, Modified Thorington Test at distance and near
1.1.13	Pupil size	Measure pupil size OD/OS in dim and bright light settings
1.1.14	Slit Lamp Exam with NaFl staining	Instill 1 drop of NaFL and evaluate slit lamp findings using the CCLRU grading scale
1.1.15	Check of eligibility and lens order randomization	Confirm eligibility criteria are met. If so, use randomization table to determine order of lens wear
1.1.16	Contact Lens Fitting	
Fit subject in the first set of contact lenses based on randomization schedule.
 
 
• The toric lens parameters should be selected based on the manufactures fitting guide.
 
• The powers for the spherical lenses should be the vertexed spherical equivalent.
 
 
After allowing the lens to settle for 10 minutes, assess the fit using slit lamp biomicroscopy.

1.1.17	Contact Lens Over-Refraction	
Perform over-refraction using maximum plus to best visual acuity
 
 
• Perform best sphere and spherocylindrical over-refraction
 

1.1.18	Contact Lens Power Adjustment (if necessary)	Follow the manufactures fitting guide and modify contact lens power, based upon the Contact Lens Over-Refraction, if the subject gains more than 3 letters of acuity with over-

**FULL PROTOCOL TITLE:** Toric Contact Lens Performance Study

		refraction
--	--	------------

Visit 2: Contact Lens Follow Up Lens #1		
Note: Subjects should report wearing their assigned study contact lenses at least 2 hours.		
2.1	Visual Acuity	Perform Distance Snellen acuity OD/OS with the patient's study lens correction.
2.2	Contact Lens Assessment	Assess the fit using slit lamp biomicroscopy.
2.3	Contact Lens Over-Refraction	Perform over-refraction using maximum plus to best visual acuity
2.4	Contact Lens Power Adjustment (if necessary)	Follow the manufacturer's fitting guide and modify contact lens power, based upon the Contact Lens Over-Refraction, if the subject gains more than 3 letters of acuity with over-refraction 

• Perform best sphere and spherical-cylindrical over-refraction

2.5	Slit Lamp Exam with NaFL	Remove the contact lens and instill NaFL then evaluate slit lamp findings using the CCLRU grading scale

Visit 3: Outcome Lens #1		
Note: Subjects should report wearing their assigned study contact lenses at least 2 hours.		
3.1	Visual Acuity	Perform Distance Snellen acuity OD/OS with the patient's study lens correction.
3.2	Questionnaires	Administer the NAVQ to the subject
3.3	High and Low Contrast Near Visual Acuity	Measure logMAR high and low contrast acuity at near OU with high luminance
3.4	Contrast Sensitivity	Perform the contrast sensitivity test on the iPad
3.5	Radner reading test	Perform the Radner reading speed test on the iPad
3.6	Functional Vision testing with iPad	Perform the functional vision test on the iPad
3.7	Slit Lamp Exam with NaFL	Remove the contact lens and instill NaFL then evaluate slit lamp findings using the CCLRU grading scale
3.8	Contact Lens Fitting	Fit subject in the second set of contact lenses based on randomization schedule. 

• The toric lens should be selected based on the manufacturer's fitting guide.

• The powers for the spherical

**FULL PROTOCOL TITLE:** Toric Contact Lens Performance Study

		
lenses should be the vertexed spherical equivalent.
 
 
After allowing the lens to settle for 10 minutes, assess the fit using slit lamp biomicroscopy.
 

3.9	Contact Lens Over-Refraction	Perform over-refraction using maximum plus to best visual acuity
3.10	Contact Lens Power Adjustment (if necessary)	Follow the manufacturer's fitting guide and modify contact lens power, based upon the Contact Lens Over-Refraction, if the subject gains more than 3 letters of acuity with over-refraction

Visit 4: Contact Lens Follow Up Lens #2
 
Note: Subjects should report wearing their assigned study contact lenses at least 2 hours.
		
4.1	Visual Acuity	Perform Distance Snellen acuity OD/OS with the patient's study lens correction.
4.2	Contact Lens Assessment	Assess the fit using slit lamp biomicroscopy.
4.3	Contact Lens Over-Refraction	Perform over-refraction using maximum plus to best visual acuity
4.4	Contact Lens Power Adjustment (if necessary)	Modify contact lens power, based upon the Contact Lens Over-Refraction, if the subject gains more than 3 letters of acuity
4.5	Slit Lamp Exam with NaFL	Remove the contact lens and instill NaFL then evaluate slit lamp findings using the CCLRU grading scale

Visit 5: Outcome Lens #2
 
Note: Subjects should report wearing their assigned study contact lenses at least 2 hours.
		
5.1	Visual Acuity	Perform Distance Snellen acuity OD/OS with the patient's study lens correction.
5.2	Questionnaires	Administer the NAVQ to the subject
5.3	High and Low Contrast Near Visual Acuity	Measure logMAR high and low contrast acuity at near OU with high luminance
5.4	Contrast Sensitivity	Perform the contrast sensitivity test on the iPad
5.5	Radner reading test	Perform the Radner reading speed test on the iPad
5.6	Functional Vision testing with iPad	Perform the functional vision test on the iPad
5.7	Slit Lamp Exam with NaFL	Remove the contact lens and instill NaFL then evaluate slit lamp findings using the CCLRU grading scale
5.8	Study Exit	Ensure all paperwork is complete and

**FULL PROTOCOL TITLE:** Toric Contact Lens Performance Study

	exit the subject from the study.
--	----------------------------------

Layman's Description of Procedures	
Patient demographics	The subjects will be asked questions about their age, sex, race and ethnicity.
History	The subjects will be asked questions about their systemic and eye health and surgical history. The subjects will be asked questions about how they use their current contact lenses, such as their current contact lens brand and wear time, as performed during a normal eye exam.
Concomitant Medications	The subjects will be asked questions about their current ocular and systemic medications.
Visual acuity and contrast sensitivity	Measurements of how well subjects can detect letters/lines and with varying levels of contrast (black versus grey on light background)
Auto-refraction/keratometry	A machine will shine light into a subject's eye and will estimate their prescription and curvature of the eye without making contact with the eye.
Slit Lamp Exam	A specialized microscope is used to shine light on the eye and to examine the health of the front of the eye. Sodium fluorescein (NaFl) is a temporary dye that is used in routine contact lens exams to evaluate the health of the front surface cells.
Refraction	The subject's prescription is determined by placing different power lenses in front of the subject's eye, and modified according to the subject's responses.
Contact Lens Fitting	A contact lens is placed on the eye and the fit is assessed (how much it moves, where it sits on the eye, etc.). This is done using a slit lamp biomicroscope.
Contact Lens Over-Refraction and Power Adjustment	Lenses will be placed in front of the subject's eye while wearing the study contact lenses to determine if the prescription needs to be changed according to the subject's responses. The contact lens power will be adjusted if needed based on standard clinical fitting guidelines.
Questionnaires	Asks the subject about his/her vision
Radner Reading and functional vision tests	Measure reading performance (speed, accuracy, etc.) using an iPad based app.

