### **9.0 Drugs or Devices**

No investigational drugs or devices will be used in this study. The contact lenses fit in the study are commercially available, FDA approved contact lenses that will be worn on a daily wear, daily disposable basis. An assistant will mask (over-label) contact lenses so that the subject and outcome examiner remain masked. The primary examiner will follow the manufacturer's fitting guide to determine the initial lens powers. Lens powers will be modified, as needed for best vision, according to the manufacturer's fitting guide.

The ophthalmic dye used in the trial to evaluate the health of the front surface (sodium fluorescein) is a commercially available ocular diagnostic agent commonly used in routine clinical assessment of contact lenses in optometry.

Study Arm	Study Contact Lenses (Alcon)	Base Curve	Diameter
Toric/Astigmatic	Dailies Aqua Comfort Plus Toric	8.8	14.4
	Dailies Aqua Comfort Plus Sphere	8.7	14.0

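### Does the different over-refraction wording for lens #1 and lens #2 bias the toric-versus-sphere comparison?

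*Protocol*

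**What the plan says.** All four fitting and follow-up visits in Protocol section 7.0 share one over-refraction sentence, "Perform over-refraction using maximum plus to best visual acuity" (steps 1.1.17, 2.3, 3.9 and 4.3). They also share one threshold for changing lens power, a gain of more than 3 letters.

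For lens #1, step 1.1.17 adds "Perform best sphere and spherocylindrical over-refraction". Step 2.4, the power-adjustment row at Visit 2, adds "Perform best sphere and spherical-cylindrical over-refraction". Neither addition appears in the lens #2 rows (3.9, 3.10, 4.3, 4.4).

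Step 3.10 says "Follow the manufacturer's fitting guide and modify contact lens power, based upon the Contact Lens Over-Refraction", as steps 1.1.18 and 2.4 do apart from a spelling difference in 1.1.18. Step 4.4 leaves out the fitting guide and says only to "modify contact lens power, based upon the Contact Lens Over-Refraction, if the subject gains more than 3 letters of acuity".

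Two general statements apply to every study lens in either period. The lay description in section 7.0 says "The contact lens power will be adjusted if needed based on standard clinical fitting guidelines", and section 9.0 says "Lens powers will be modified, as needed for best vision, according to the manufacturer's fitting guide".

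Section 4.0 allocates equal numbers to the two lens orders. The SAP fits period and sequence in a mixed model for outcomes analysed parametrically, tests carry-over at 0.10, and tests on period 1 alone if carry-over is found.

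**The concern.** The trial compares a lens that corrects cylinder with one that does not, in people with 0.75 to 1.50 D of refractive cylinder. The instruction that differs between periods is the one that names a cylinder check. Read literally, lens #1 is refined with a best-sphere and spherocylindrical over-refraction, while lens #2 has only the maximum-plus sentence.

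If that reading were true and the fuller check mattered more for one lens type than the other, the lens effect would differ between periods. In a two-period, two-sequence crossover such a treatment-by-period interaction is aliased with carry-over. Fitting period and sequence does not remove it, and the SAP's 0.10 test has little power to reveal it. The pooled toric benefit on binocular near acuity would then be shifted.

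**Working it through.** **Step 1: set the rows side by side.**

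| Step | Lens | Maximum-plus sentence | Sphere/spherocylindrical line | Fitting guide cited | More than 3 letters |
|---|---|---|---|---|---|
| 1.1.17-1.1.18 | #1 | yes | yes (1.1.17) | yes | yes |
| 2.3-2.4 | #1 | yes | yes (2.4, adjustment row) | yes | yes |
| 3.9-3.10 | #2 | yes | no | yes | yes |
| 4.3-4.4 | #2 | yes | no | no | yes |

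Two differences appear. The missing fitting guide in 4.4 is covered by section 9.0, which applies the guide to power changes in general. The missing sphere/spherocylindrical line is not supplied elsewhere in the documents.

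**Step 2: intent or slip?**

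- Step 2.3, for lens #1, has the same bare sentence as 3.9 and 4.3, so the bare sentence is not peculiar to lens #2.
- The extra line at Visit 2 stands in the adjustment row rather than the over-refraction row. That suggests loose drafting, although table extraction may have moved it.
- The maximum-plus phrase does not exclude cylinder. Step 1.1.11 uses it for the full manifest refraction: "Perform Manifest Refraction using maximum plus to best visual acuity".
- The lay description and section 9.0 describe one procedure without reference to period, and nothing says the periods were meant to differ.
- The fitting guide cited in 3.10 and section 9.0 may specify the over-refraction. It is not among the documents, so this cannot be checked.

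**Step 3: what if the tables were followed literally?** Score acuity so that larger is better. Let D be the toric benefit under the lens #1 procedure, p a period-2 shift common to both lenses, and g and s the period-2 losses confined to a toric and to a spherical lens.

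- Toric first: toric minus sphere = D − p + s
- Sphere first: toric minus sphere = D + p − g
- Mean of the two sequences = D + (s − g)/2
- Difference in sequence totals (what the carry-over test examines) = g − s

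The common shift p drops out. With D = 0.050 logMAR (the half-line benefit in section 4.0) and assumed losses:

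| g | s | Pooled estimate |
|---|---|---|
| 0 | 0 | 0.050 |
| 0.02 | 0.02 | 0.050 |
| 0.02 | 0 | 0.050 − 0.010 = 0.040 |
| 0 | 0.02 | 0.050 + 0.010 = 0.060 |

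The sign is not fixed. The omitted line names best sphere as well as spherocylindrical refinement, so a loss could fall on either lens type.

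**Step 4: illustrative power, toric-only loss.** The plan's own figure first: n = 34, difference 0.05, SD of the difference 0.10 (section 4.0 calls this a variance; it is read here as an SD) and two-sided α = 0.05 give 80.8% power by the paired t-test. The stated 34 for 80% therefore reproduces.

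For g = 0.01, 0.02 and 0.03 the expected effects are 0.045, 0.040 and 0.035, and paired-t power is 72%, 62% and 51%. Under the SAP's two-stage rule (simulated with 17 per sequence and assumed within-subject correlations of 0.3 and 0.7), power is about 78% at g = 0, then 71-72%, 63-64% and 54-56%. At g = 0.02 the carry-over test rejects in about 11-13% of trials, against 10% under no effect. Every value of g here is assumed.

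**The case for a change.** The strongest case for acting is that a reader cannot tell from the documents whether both lenses received the same over-refraction, and that the item in doubt bears directly on what is being compared. The general statements on lens power do not name the over-refraction type. An interaction of this kind would survive the period and sequence terms and would usually pass the carry-over test. Aligning four tables, or adding one sentence to the report, costs almost nothing.

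Part of this stands. The passages do not agree and should read alike, and which version applies is for the sponsor to say. The aliasing argument is correct, and so is the low power of the carry-over test at g = 0.02.

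What does not stand is the step from there to a threat to the result. It needs three things in turn: that examiners followed the tables literally despite the general rule, that refinement at lens #2 was poorer as a result, and that the loss differed by lens type and reached binocular near acuity. The documents support none of these. Nor can it be argued that any bias must run against the toric lens: with a loss on the sphere the estimate rises. The power figures show only what follows from a chosen g.

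**Conclusion.** No change to the plan follows. The over-refraction wording differs between lens #1 and lens #2, most probably through a drafting slip; the omission of the fitting guide in step 4.4 is covered by section 9.0.

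If staff applied one over-refraction routine throughout, as the general statements suggest, the effect on the comparison is nil. If they followed the tables literally, a shift common to both lenses cancels, because the sequences are planned to be equal and period is in the model. A lens-specific difference would move the pooled toric benefit by (s − g)/2, which is 0.010 logMAR in either direction for an assumed 0.02 loss on one lens type alone. The documents give no size or sign for such a loss.

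This conclusion rests on equal sequences and on reading the maximum-plus sentence as not excluding cylinder. Reconciling the rows is editorial tidying that leaves the randomisation, endpoint, sample size and analysis as they are.
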